**Randomization:** After informed consent and screening are completed, participants meeting study inclusion/exclusion criteria will be randomized (1:1) to the B-EPIC group (tobacco intervention) or TAU tobacco treatment (control group). All will continue to receive opioid dependence treatment with buprenorphine, regardless of treatment assignment. Randomization will be stratified by age (30+ vs less than 30). We will create a separate randomization schedule for each age stratum using the PLAN procedure in SAS (SAS Institute, Inc.); each schedule will include 17 blocks of 6 participants, with half per block randomized to each of the two treatment groups. Recruitment in this fashion will ensure an approximately equal number of subjects in each group throughout the enrollment period in both age strata, and we will continue recruitment until we have enrolled 100 subjects.

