### Statistical Analysis Plan

One hundred pregnant women undergoing medically-assisted treatment (MAT) with buprenorphine for opioid dependence will be recruited and randomized to B-EPIC ( $n=50$ ) or TAU ( $n=50$ ).

**Data Analysis (to determine the impact of the B-EPIC intervention on smoking indicators as well as birth and infant outcomes; Aims 1-2).** Data analyses will be done using SAS 9.4, with an alpha level of .05; analyses for these two aims will be done by [name]. Descriptive analysis, including means and standard deviations or frequency distributions, will be used to summarize all study variables. Baseline comparisons of covariates between the intervention group and the control, and between those who complete the study and those who drop out will be done using t-sample t-tests, Mann-Whitney U tests, or chi-square tests of association. Primary outcomes to be compared between treatment groups will include tobacco indicators, such as smoking and illicit drug use status (abstinence via urine cotinine, iCup results), smoking frequency and readiness to quit (cigarettes per day and stages of change), and maternal-child measures (gestational age of birth, birthweight, NAS, NAS severity, early childhood respiratory and ear infections). The collected variables will include not only these primary outcomes and covariates, but also feasibility indicators, such as average number of sessions completed and ratings of intervention by participants randomized to the intervention group. We will also make group comparisons between other variables that may affect maternal-child outcomes, including SHS exposure, infant feeding status at discharge (breastfeeding vs. formula), and number of people in the home. Those factors with group differences (including demographic factors measured at baseline) will be used as covariates in the corresponding analysis of group comparisons of maternal-child outcomes over time. The primary analysis strategy for the first

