two study aims will be two-factor (group x time) repeated measures mixed models; these will be estimated using the MIXED procedure or group comparisons of continuous outcomes over time, including cigarette use and tobacco dependence. Generalized estimating equation (GEE), analyses with an exchangeable correlation structure will be used to assess for significant differences between groups and across time for categorical and dichotomous outcomes (e.g., preterm birth, NAS) using the SAS GENMOD procedure. The main effects of group and time and the interaction between them will be included in each model, and covariates will be added to control for group differences. As appropriate, post-hoc pairwise comparisons will be done using Fisher's least significant difference procedure for mixed models and using contrast statements for GEE models.

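### Randomisation is stratified by age, but no Aim 1–2 model is guaranteed to include the stratum, so some group comparisons are mildly conservative if age group predicts outcome

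*Combined protocol and SAP*

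**What the plan says.** - **Design.** Study Procedures, Randomization: "Randomization will be stratified by age (30+ vs less than 30". There is one schedule per age stratum, and "each schedule will include 17 blocks of 6 participants, with half per block randomized to each of the two treatment groups". The target is 100 women, 50 per group.
- **Models.** Statistical Analysis Plan, Data Analysis (Aims 1–2): mixed models for continuous outcomes and GEE for categorical ones. Each holds the group and time main effects and their interaction, which "will be included in each model, and covariates will be added to control for group differences".
- **Covariate rule.** The same section says "Those factors with group differences (including demographic factors measured at baseline) will be used as covariates". That sentence concerns maternal-child outcomes, and it sets no threshold for a group difference. Baseline comparisons use t-tests, Mann-Whitney or chi-square tests, and the section opens with "Data analyses will be done using SAS 9.4, with an alpha level of .05".
- **Age as a covariate.** The Covariates paragraph under Measures lists age in years among the demographic covariates. It does not mention the two-level randomisation stratum.
- **Power.** Power Considerations gives 79% for the group main effect at a medium effect size (ratio 0.25) with 30 completers per group, and 60% at a ratio of 0.20. For logistic regression at an odds ratio of 2.5 it gives 68%.

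**The concern.** The factor chosen for stratification has no assured place in the analysis, and the stated route into a model works against it. Covariates enter because the groups differ on them, and stratified blocking exists to stop the groups differing on age.

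This matters only if age group is related to the outcome. Stratified allocation then removes between-stratum variation from the real sampling error of the treatment difference, while a model without the stratum leaves that variation in its residual. The standard error comes out too large, the test rejects less often than its nominal level, and some power is given away. Power is already modest here, and the plan says its main emphasis is estimating effect sizes for later trials, so interval width counts.

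**Working it through.** **1. Reproducing the plan's power.** Inputs from Power Considerations: N = 60 completers, m = 4 time-points, f = 0.25, alpha .05 (taken as two-sided). The within-woman correlation ρ is not given; ρ = 0.3 is inferred because it recovers the stated figures.

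λ = f²·N·m / (1 + (m−1)ρ) = 0.0625 × 60 × 4 / 1.9 = 7.89. On 1 and 58 df, power is 78.9% (stated 79%). At f = 0.20, λ = 5.05 and power is 59.9% (stated 60%).

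**2. Can a difference-based rule select the stratum?** Only the last, incomplete block of each schedule can be unbalanced, so the arms differ by at most 3 women per stratum. Enumerating every allocation of 100 women, for every split between strata (chi-square without continuity correction):

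- Most extreme case: a stratum of 3 women, all in one arm (0 v 3; other stratum 49 v 48). χ² = 100 × (0×48 − 49×3)² / (49×51×3×97) = 2.97, p = 0.085.
- With at least 20 women in each stratum, the most extreme is 9 v 12 and 40 v 39. χ² = 100 × (9×39 − 40×12)² / (49×51×21×79) = 0.40, p = 0.53.

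At .05 the stratum can never be selected. Age in years fares little better. With age assumed roughly normal (mean 27–30, SD 4–5), simulation found a difference in 0.1–0.3% of trials at p<.05, 0.7–2.3% at p<.10 and 3.5–6.9% at p<.20.

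**3. Cost for the group main effect and single-time continuous outcomes.** Let R² be the share of between-woman variance in the compared quantity that the stratum explains (assumed). The SE ratio, without v with the stratum, is 1/√(1−R²). Approximate type I error without the stratum is 2Φ(−1.96/√(1−R²)). Calculated power with the stratum uses λ/(1−R²) on 1 and 57 df.

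| R² | SE ratio | Type I, formula (simulated) | Power with stratum, f = 0.25 |
|---|---|---|---|
| 0 | 1.000 | .050 (.050) | 78.9% |
| 2% | 1.010 | .048 (.049) | 79.7% |
| 5% | 1.026 | .044 (.046) | 80.9% |
| 10% | 1.054 | .039 (.040) | 82.9% |

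The power column flatters the gain a little, because stratified allocation has already narrowed the sampling distribution and so helps the unadjusted test too. Simulating one outcome with a 0.6 SD effect gave 84.3% without v 85.9% with the stratum at R² = 5%, and 86.1% v 88.4% at R² = 10%.

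**4. Group-by-time contrast.** A stratum effect that is constant over time cancels from a within-woman change. Simulation used 100 women, four times, ρ = 0.3, complete data and age gaps of 0.4, 0.6 and 0.8 SD. The SE ratio for the post-minus-baseline contrast was 1.000 throughout. For the four-visit group mean it was 1.04, 1.09 and 1.15. These exceed the table because, assuming 40% of women are 30 or over, the gaps imply R² = 0.24δ²/(0.24δ² + 1.9/4) = 7.5%, 15.4% and 24.4%.

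**5. Binary outcomes.** Unadjusted comparison of two proportions under the null, stratified blocks, 100 women (model SE over true SD; rejection rate):

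- Risks 10% v 20% by stratum: 0.99; .054.
- 10% v 40%: 1.04; .043.
- 20% v 60%: 1.08; .038.

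**The case against.** A reader might infer that the plan keeps age out of every model. The text does not say so. Age in years is a listed covariate, baseline demographic factors may enter, the explicit selection rule covers maternal-child outcomes only, and no significance threshold is set. The sentence on model terms can also be read as adding the listed covariates. What the documents support is narrower: inclusion of the stratum is not guaranteed, and a rule based on differences would hardly ever trigger it.

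A reader might also infer that all tests and intervals are too wide. That too goes beyond the documents, which say nothing about how strongly age group predicts any outcome. The comparison over time from baseline is the natural reading of the treatment effect for repeated tobacco measures, and it is essentially untouched by a constant stratum effect. For binary outcomes a large difference in risk between age groups is needed before anything shows.

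Finally, the error is in the safe direction, and this is a declared pilot that already concedes group differences may not be detectable. All of this stands. It limits the size of the point but gives no reason to leave the stratum out.

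**Conclusion.** The point holds in limited form. The design stratifies on age, no Aim 1–2 model is certain to contain the stratum, and the covariate rule works against including it. If age group is prognostic, inference on group main effects and single-time outcomes such as gestational age and birthweight is somewhat conservative. The SE excess is about 1–5% for R² of 2–10%, and at most about 4 power points are forgone. At R² = 0 the loss is nil. There is no bias and no excess of false positives.

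These sizes rest on assumed R² values and an inferred correlation of 0.3. The near-certainty of non-selection assumes the rule is applied as a significance screen; for the binary stratum at .05 it then follows from the block design alone. This is a free improvement, not a threat to the trial's validity.

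**What to change.** In the Statistical Analysis Plan, Data Analysis (Aims 1–2), after the sentence on model terms, add: *Every MIXED and GEE model for Aims 1 and 2 includes the randomisation age stratum (30+ vs under 30, as randomised) as a fixed effect, whether or not the groups differ on it.*

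The cost is one sentence and one degree of freedom per model. The stratum is known for every woman at randomisation, so no data are lost. In logistic GEE models the odds ratio becomes conditional on age group, which the report should state. The sentence also removes a choice that would otherwise be made after seeing the baseline table.

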**Table 2. Estimated retention at each perinatal period**

	2 nd Trimester (18-24 weeks)	3 rd Trimester (30-36 weeks)	Postpartum (1-2 months)	Postpartum (5-6 months)
Usual Care	50	45	39	28
B-EPIC	50	45	39	28
Total	100	90	78	56

**Inclusion criteria:** 1) current diagnosis of opioid dependence with participation in the buprenorphine treatment program; 2) less than 32 weeks gestation; 3) age 18-49 years old; 4) diagnosis of current tobacco use disorder; and 5) read or write in English. **Exclusion criteria:** Women are excluded if they have current prisoner status, current severe mental illness (e.g., bipolar disorder with current mania, current suicidal ideation), or alcohol or sedative/hypnotic dependence that requires medical intervention.

**Recruitment, Screening and Informed Consent:** Institutional Review Board (IRB) approval will be obtained from the University of Kentucky for this study. The screening, recruitment and retention plan is anchored by our previous work among pregnant and postpartum women who smoke. All study personnel will have completed human subjects training - and good clinical practice (GCP) research training. There will be two methods of recruitment: 1) study flyers will be posted in highly visible areas in the UKHC MAT clinics for pregnant/postpartum women and 2) the research nurse will provide an overview of the B-EPIC study in the buprenorphine treatment clinic for pregnant women. At conclusion of the overview, all women will be given a flyer in which they can either check that they are interested in screening for the study, verbally let the research nurse know they are interested in screening, and also be given the study recruitment phone number. Volunteers interested in the study will be screened for eligibility by research staff and those meeting initial eligibility screening criteria will be invited to come in for an in-person screening whereby informed consent will be completed before any study procedures are initiated (see Human Subjects).

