**Handling Missing Data.** Based on our prior longitudinal studies with pregnant and postpartum women, we anticipate retention to be at least 60% (9-12% attrition from 2nd-3rd trimester through 1-2 months postpartum; additional 30% attrition to 5-6 month postpartum), as shown in Table 2. The power estimates outlined below are expected to be conservative for several reasons: 1) attrition in the current UKHC MAT program is 12%; 2) we will use escalating and completion incentives to encourage completion; and 3) increased options for follow-up communication (email, text), using each participant's preferred communication method. Maternal and infant outcome data will be extracted from the UKHC medical record and national MEPS, reducing participant burden. Nonetheless, missing data will occur in this vulnerable population and we acknowledge this in the analysis, given that our analysis strategies allow for inclusion of participants who are missing one or more assessments. We will use the intention to treat convention (those randomized to the B-EPIC group will be retained in this group in the analysis whether or not they complete the entirety of the intervention). For the tobacco use indicators, we will examine group differences assuming the last observation carried forward (LOCF; e.g., if a participant is an active smoker at one time-point, we will assume this status at future time-point(s), if she drops out). We will conduct initial analyses using the maximum likelihood approach, as it emphasizes the use of all available data. The use of random effects modeling techniques, including repeated measures mixed modeling, allows for missing data by adjusting the estimation process to account for bias resulting from data missing at random. In addition, multiple imputation will be used as an alternative procedure for handling missing data. Multiple imputation produces results similar to maximum likelihood when used under identical conditions. The strategy of observing differences in group comparisons under these two methods of dealing with missing data is suggested by Hedeker et al. as a way to determine the robustness of the results under these different assumptions. This approach will provide a sensitivity analysis of the group comparisons.

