**Power Considerations.** With approximately 50 per group and an alpha level of .05, the power of the two-sample t-test to detect a baseline group difference in a continuous covariate will be at least 84% if the ratio of the difference in means to the standard deviation is at least 0.6. This is slightly larger than a medium effect size. With approximately 50 per group and a .05 level of significance, the power of the chi-square test of association to detect an odds ratio as small as 3.5 will be at least 81%. One way to obtain an odds ratio of this magnitude would be if the prevalence of a given binary covariate at baseline were 60% in one group and 30% in the other. With at least 30 mother/baby dyads completing the study per group and an alpha level of .05, the power of the repeated measures analysis of variance F test to detect a significant main for group will be 79%, assuming a medium effect size, while the power of the F tests to detect a significant main effect of time or group by time interaction will be at least 95%, under these conditions. In the context of repeated measures modeling, a medium effect size is one such that the ratio of the standard deviation of the group means to the standard deviation of the observations within the populations is at least 0.25. Even if this ratio is smaller than a medium

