effect (i.e., 0.20), the power of the repeated measures mixed model will be at least 60% to detect a group effect and 87% to detect a time or interaction effect. While an algorithm for estimating the power associated with a generic GEE model has not been developed, this strategy is analogous to a repeated measures application of logistic modeling. With at least 60 mother/baby dyads completing the study and an alpha level of .05, the power of logistic regression to detect an odds ratio of 2.5 or larger will be at least 68%. While this level of power is not optimal, inclusion of 4 time-points in the GEE models will increase the power of this analysis technique relative to a logistic model for a fixed point in time; this phenomenon is consistent with the comparison of the expected power of a two-sample t-test relative to expected power of a repeated measures comparison of two groups over 4 time-points, namely power for the later exceeds the former under the same conditions. Given the paucity of research regarding tobacco cessation in this at-risk population, it is unknown whether a medium (or slightly smaller) effect size is appropriate for continuous outcomes, such as cigarettes per day. However, in a preliminary study of this population by our group (EMPOWR, described above), we found that 14% of pregnant women decreased their cigarette consumption between intake (typically during the second trimester) and the third trimester. This is notable since each participant chose a health goal to work on (including reducing stress, reducing alcohol/drug use, reducing smoking, or weight management), so not all would have focused on decreasing cigarette consumption. While smoking cessation is the ultimate goal of this intervention, prior research has demonstrated that cutting cigarette consumption below 8 cigarettes per day is a risk reduction strategy for preventing low birthweight, so we will consider outcomes of both successful cessation as well as reduction in consumption for this exploratory project. In addition, a prior study (using a different cessation intervention but with a similar sample size) has demonstrated that while pregnant women addicted to opioids were not able to quit smoking at a higher rate than those not exposed to the intervention, there was a significant increase in readiness to quit, as assessed via stage of change, in the intervention group relative to the controls. We are assessing changes in stage of change over time between the groups for this reason. For all of the inferential tests used in this study, the primary emphasis of these group comparisons will be to estimate effect sizes for the impact of the intervention, which will allow us to estimate power for future (larger) studies. We expect to be able to demonstrate group differences with this exploratory study, given the relatively modest effect sizes required to have a reasonable level of power to detect differences in outcomes between groups. As outlined above, the estimated effect sizes for the longitudinal analyses are expected to be conservative, given that they are based on the minimum expected sample size at the completion of the study; however, since the repeated measures modeling allows for the inclusion of participants who drop out prior to completion, the effective sizes for these group comparisons over time are actually underestimated.

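### The plan claims at least 60% retention and a minimum of 30 completing dyads per group, but the table it cites projects 56% and 28

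*Combined protocol and SAP*

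**What the plan says.** Enrolment is 100 women, 50 per group, randomized 1:1 (Statistical Analysis Plan, opening paragraph; Randomization).

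Handling Missing Data states "we anticipate retention to be at least 60" per cent and points to Table 2. It breaks the loss down as "9-12% attrition from 2 nd -3 rd trimester through 1-2 months postpartum", then "additional 30% attrition to 5-6 month postpartum".

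Table 2 ("Estimated retention at each perinatal period") gives, for each group, 50 at the second trimester, 45 at the third, 39 at 1-2 months postpartum and 28 at 5-6 months. The totals are 100, 90, 78 and 56.

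Power Considerations begins its repeated-measures figures "With at least 30 mother/baby dyads completing the study per group" and reports 79% power for the group effect at an effect ratio of 0.25, and at least 95% for time or interaction. At 0.20 it reports at least 60% and 87%. The logistic figure, 68% for an odds ratio of 2.5, uses 60 dyads. The paragraph closes by calling the longitudinal estimates conservative because "they are based on the minimum expected sample size at the completion of the study".

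**The concern.** A floor of 60% cannot be supported by a cited table that shows 56%, and 30 per group cannot be the minimum when the plan projects 28. The plan presents its power figures as a worst case, and on its own projection the completer count behind them is not one.

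What is at stake is modest. The 5-6 month visit carries the later part of the after-pregnancy comparison in Aim 1. The study is also a pilot meant to test feasibility and inform a larger trial, so its retention assumption may be reused in planning that trial.

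**Working it through.** **Retention from Table 2.**
- Final retention: 28/50 = 56/100 = 56.0%.
- Interval losses: 5/50 = 10.0%, 6/45 = 13.3%, 11/39 = 28.2%. The middle one lies outside the stated 9-12%.

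**Retention from the attrition text.** The wording does not say whether 9-12% is lost once or at each of two intervals.
- Once, then 30%: 0.88 × 0.70 = 61.6% to 0.91 × 0.70 = 63.7%. This supports the 60% floor, but it implies 88 to 91 women at 1-2 months, where Table 2 has 78.
- At each of two intervals, then 30%: 0.88² × 0.70 = 54.2% to 0.91² × 0.70 = 58.0%. Taking 9% then 12% gives 0.91 × 0.88 × 0.70 = 56.1%, which matches Table 2's endpoint.

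No single reading yields both the 60% floor and Table 2.

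**Reproducing the stated power.** Two groups, m = 4 visits, N completers in total, effect ratio f, between-visit correlation ρ, two-group repeated-measures F tests at 0.05:
- group effect: λ = f²Nm / [1 + (m−1)ρ], df 1 and N−2;
- interaction: λ = f²Nm / (1−ρ), df 3 and 3(N−2).

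The documents give no ρ. Solving for 79% at N = 60 and f = 0.25 gives ρ ≈ 0.298: λ = 0.0625 × 60 × 4 / 1.894 = 7.92. The same ρ gives 60.0% at f = 0.20, and interaction power of 98.0% and 88.1%, in line with the stated figures of at least 95% and 87%. So the stated figures are consistent with 30 completers per group.

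**Completers only, at Table 2's count (N = 56, ρ ≈ 0.298).**

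| Effect | f | Stated | N = 60 | N = 56 |
|---|---|---|---|---|
| Group | 0.25 | 79% | 79.0% | 76.1% |
| Group | 0.20 | at least 60% | 60.0% | 57.0% |
| Interaction | 0.25 | at least 95% | 98.0% | 97.2% |
| Interaction | 0.20 | 87% | 88.1% | 85.5% |

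The group-effect loss at f = 0.25 is 1 to 3 points for ρ from 0 to 0.7 (96.8% to 95.7% at ρ = 0; 58.1% to 55.1% at ρ = 0.7).

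**Planned mixed model, with partial data.** Assume monotone dropout in Table 2's pattern (50/45/39/28 per group), data missing at random, and equal correlation between visits. For each dropout pattern, add the inverse covariance of the observed visits, weighted by the number of women, and invert the sum. At ρ ≈ 0.298 the variance of one group's four-visit mean is 0.01099 (unit outcome variance). A four-visit completer contributes (1 + 3ρ)/4 = 0.4735, so the pattern is worth 0.4735/0.01099 ≈ 43 completers per group. Then λ = 0.0625 × 86.2 × 4 / 1.894 = 11.4, and power is 91-92% at f = 0.25 and about 76% at f = 0.20, depending slightly on the degrees of freedom. At ρ = 0.5 it is about 84-85% and 66-67%.

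The interaction gains less. The least precise time contrast has variance 0.0240, against 0.702/30 = 0.0234 for 30 completers and 0.702/28 = 0.0251 for 28. The other two contrasts are more precise than with 30 completers.

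**Logistic figure.** The 68% cannot be reproduced, because neither the event rate nor the type of covariate is given. As an illustration, for a standardized continuous covariate, power = Φ(√[N·P(1−P)] × ln 2.5 − 1.96). At an assumed event rate P = 14%, it falls from 69% (N = 60) to 66% (N = 56). Over P from 10% to 50% the loss is about 1.5 to 3 points.

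**The case against.** The strongest reply is that the plan does not analyse completers only. It specifies mixed models fitted by maximum likelihood, and Power Considerations itself says that women who drop out still contribute. A reader might infer from the shortfall that the trial is underpowered against its stated figures. The documents do not support that: under Table 2's own pattern, group-effect power averaged over visits stays above 79% and 60% at correlations of 0.30 and 0.5. This part of the reply stands for the group effect, under the assumptions stated above. It does not make 30 the expected minimum, and it does not cover the logistic figure, which the plan ties to 60 completing dyads at a fixed time.

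A second reply is that Table 2 may be the side in error, since 9-12% applied once supports 60%. That is possible, and the text alone cannot settle it. But Table 2 is the only visit-by-visit projection, and the text cites it as its source.

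A third reply is that gestational age, birthweight and NAS are birth outcomes, and that maternal and infant outcomes are to come from medical records and national survey data. This also stands: attendance at 5-6 months does not set the yield for much of Aims 2 and 3. The plan also describes itself as exploratory, with emphasis on estimating effect sizes.

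**Conclusion.** The inconsistency is real and can be seen in the documents without assumptions: 56% against at least 60%, 28 per group against at least 30, 56 dyads against 60, and a minimum that exceeds the projection. Its consequence is small. On a completers-only basis the group-effect power drops about 3 points (79% to about 76%; 60% to about 57%), interaction power at 0.20 is about 86% against the stated 87%, and the 95% figure at 0.25 still holds. These power figures rest on an inferred correlation of about 0.30. They describe a completers-only analysis, so they are not evidence that the planned mixed model is underpowered for the group effect. Severity is minor.

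**What to change.** Reconcile Handling Missing Data and Power Considerations with Table 2. Unless the sponsor shows that Table 2 is wrong, in which case the table should be corrected:

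- State expected retention to 5-6 months as 56% (28 per group, 56 dyads).
- Say whether the 9-12% attrition applies once or at each interval, and align it with Table 2's losses of 10.0%, 13.3% and 28.2%.
- Stop describing 30 per group as the minimum expected number at completion.
- Restate the completer-based power at 28 per group with the assumed correlation given, labelled as completers-only. If the sponsor wishes, add the mixed-model power under the Table 2 pattern.
- Recompute the fixed-time logistic figure at 56 dyads, stating the event rate and the type of covariate.

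The cost is rewording and a short recalculation. Enrolment, visits and the analysis methods do not change.

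### For continuous visit-based outcomes, the planned comparison of maximum likelihood with multiple imputation is not a sensitivity analysis for dropout: both assume data missing at random

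*Combined protocol and SAP*

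**What the plan says.** In the Statistical Analysis Plan, the paragraph headed Handling Missing Data makes ML the initial analysis and justifies it for data missing at random. It adds MI as an alternative and remarks: "Multiple imputation produces results similar to maximum likelihood when used under identical conditions". The next sentence presents the comparison of the two methods "as a way to determine the robustness of the results under these different assumptions", and the paragraph ends by calling this a sensitivity analysis of the group comparisons. No shift, reference-based rule, pattern-mixture model or other departure from MAR is given for the MI, and no imputation model is described.

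The same paragraph plans LOCF for the tobacco use indicators. Its example is a smoker who drops out and is kept as a smoker.

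The paragraph on data analysis for Aims 1-2 assigns continuous outcomes to mixed models, and categorical and dichotomous outcomes to GEE with an exchangeable correlation.

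Table 2 expects 50, 45, 39 and 28 women per arm at the four visits.

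**The concern.** A sensitivity analysis for dropout has to change the assumption about the women who are not seen. Here that assumption concerns whether, given what was observed earlier, women who leave smoke as much as similar women who stay. ML in a mixed model and standard MI both assume that they do. If heavier smokers or relapsed women leave, both estimates shift together, and their agreement would be reported as robustness.

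Two features make this worth correcting. Planned loss is large. Contact also differs by arm: B-EPIC adds tobacco treatment at least monthly with biomarker feedback, while TAU gives brief advice at appointments, so reasons for leaving could differ between arms. Power Considerations says the main emphasis is on estimating effect sizes for planning larger trials. A biased estimate described as robust would carry into that planning.

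**Working it through.** **1. How much is missing.** The text says "we anticipate retention to be at least 60" per cent and refers to Table 2. The table gives 28/50 = 56% retained, so 22/50 = 44% missing at 5-6 months. Its steps are 1 - 45/50 = 10.0%, 1 - 39/45 = 13.3% and 1 - 28/39 = 28.2%. The text's 9-12% loss followed by an "additional 30% attrition to 5-6 month postpartum" gives 0.88 × 0.70 = 61.6% to 0.91 × 0.70 = 63.7% if 9-12% is one step. If it applies at two steps, the result is 0.88² × 0.70 = 54.2% to 0.91² × 0.70 = 58.0%. I use the table's 44%; at 60% retention the multiplier in step 3 would be 0.40.

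**2. What each planned analysis assumes about dropout.**

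| Outcome type | Main analysis | Alternative | What the comparison varies |
|---|---|---|---|
| Continuous (cigarettes per day, dependence) | ML mixed model: MAR | MI: MAR | Nothing |
| Binary or categorical (cotinine abstinence, stage of change) | Unweighted GEE: generally missing completely at random | MI: MAR | Missing completely at random to MAR only |
| Tobacco use indicators | As above | LOCF: no change after last visit | A departure from MAR, but outside the ML-MI comparison |

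**3. Why ML and MI share the bias.** Let p be the share missing at the final visit. Let δ be the amount by which an arm's dropouts truly exceed their MAR prediction. Either method misses that arm's mean by -p × δ, so

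bias in the group difference = -p × (δ in B-EPIC - δ in TAU).

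For example, a between-arm difference in δ of 3 cigarettes per day gives 0.44 × 3 = 1.3 cigarettes per day of false benefit. ML and MI use the same prediction; MI adds only imputation noise.

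**4. Simulation, one baseline and one final visit.** Assumed inputs, none from the documents: SD 8 cigarettes per day, baseline-final correlation 0.5, no true effect. From Table 2: 28 of 50 observed per arm. Dropout depends on the current, unobserved value.

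| Dependence of dropout on current smoking | False benefit, cigarettes per day (ML and MI alike) |
|---|---|
| Equal in both arms | about 0 |
| Moderate in both, stronger in B-EPIC (0.6 versus 0.4) | about 0.7-0.9 |
| Moderate, B-EPIC only (0.4) | about 1.6 |
| Strong, B-EPIC only (0.8) | about 2.7-3.6 |

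The ranges reflect whether the strength is coded as a coefficient with unit noise (lower figure) or as a correlation (higher figure). By the formula, 1.6 corresponds to a δ difference of 1.6/0.44 = 3.6, and 2.7 to 2.7/0.44 = 6.1 cigarettes per day. At the lower coding of the last row, B-EPIC dropouts smoke about 8 per day (1 SD) more than those who stay. Within a trial, ML and MI differ by about 0.15 cigarettes per day on average, whatever the shared bias.

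**5. Simulation, four visits with Table 2 dropout.** Correlation 0.5, no true effect, 300 trials. Under random dropout, ML and MI each gave -0.02 SD. With dropout in B-EPIC alone driven by the current value, ML and MI each gave -0.30 SD (0.30 × 8 = 2.4 cigarettes per day at SD 8), and LOCF gave -0.12 SD. ML and MI differed by about 0.03 SD in both cases (correlation 0.99). In a separate four-visit run with the strong mechanism of step 4, the ML bias was 2.0 cigarettes per day at the last visit and 0.9 averaged over visits.

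**The case against.** The strongest reply is that LOCF is planned for the very outcomes at issue. A reader might infer that the plan has no analysis outside MAR; that is not so. In the strong one-arm scenario, ML showed a false benefit of 2.8 and LOCF 1.0 cigarettes per day, so a careful reader of both results would see a gap. This stands as a limit on the point, but it does not rescue the check. The robustness statement concerns ML and MI. LOCF is one fixed assumption, carries a quitter who drops out forward as abstinent, still shows some false benefit, and comes with no rule for weighing it against ML.

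A reader might also infer that the trial will report a spurious benefit near 3 cigarettes per day. Nothing in the documents supports the one-sided dropout this needs, and equal dependence in both arms gives about 0.

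Two further readings go beyond the text. The comparison "between those who complete the study and those who drop out" is not said to pool the arms. And although "covariates will be added to control for group differences" describes the outcome models, the contents of the imputation model are not stated, so no predictor of dropout can be said to be left out of it. If MI did use extra predictors it could differ from ML, but it would still assume MAR.

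Finally, the trial is exploratory, and birth and infant outcomes taken from records are less affected.

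**Conclusion.** The point holds for continuous visit-based outcomes: the comparison presented as a test of different assumptions tests none about dropout. This follows from the shared MAR assumption and does not depend on the simulation inputs. For binary and categorical outcomes, GEE against MI does vary the assumption, but only up to MAR, so dropout that is not at random is not tested by that comparison either.

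The size is uncertain. With SD 8, correlation 0.5 and 44% loss at one visit, the false benefit runs from about 0 to about 2.7-3.6 cigarettes per day, the upper end being close to a worst case. ML remains a reasonable main analysis. The defect is in the safeguard and in the reassurance drawn from it, and should be corrected before analysis.

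**What to change.** - Delete the statement that ML against MI examines different assumptions. Keep ML as the main analysis for continuous outcomes.
- Add a delta-adjusted (tipping-point) MI. Make dropouts' imputed cigarettes per day worse over a stated range, in B-EPIC alone and in both arms, and report the shift at which the conclusion changes. Adding predictors of dropout to the imputation model may help, but it stays within MAR and does not replace this step.
- For cotinine abstinence, add an analysis that counts missing as smoking.
- State that LOCF is supplementary.
- Report dropout by arm at each visit.

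The cost is SAP wording and a little programming (the MNAR statement in SAS PROC MI). No new data, visits or participants are needed. The downside is a wider set of results to report.
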